#### **7.1.1 External Ocular Examination**

External Ocular Examination assesses the motility of the extraocular muscles and the appearance and function of the eyelids before the instillation of any dilating or anaesthetic eye drops.

#### **7.1.2 Symptom Assessment in Dry Eye (SANDE):**

The Symptom Assessment in Dry Eye (SANDE) questionnaire is a short questionnaire to evaluate both dry eye intensity and frequency by using a 100 mm VAS. The patient symptoms of ocular dryness and/or irritation will be quantified on the scale based on two questions that assess both severity and frequency of symptoms. A VAS is a measurement instrument that tries to measure a characteristic or attitude that is believed to range across a continuum of values and cannot easily be directly measured. For example, the amount of irritation that a patient feels ranges across a continuum from none to an extreme amount of irritation. From the patient's perspective this spectrum appears continuous (i.e. their irritation does not take discrete jumps, as a categorization of none, mild, moderate and severe would suggest). It was to capture this idea of an underlying continuum that the VAS was devised.

For the assessment, the patients mark on the 100 mm VAS line the point that they feel represents their perception of their current state. The VAS score is determined by measuring in millimetres from the left hand end of the line to the point that the patient marks. The SANDE scores will be then evaluated for the 2 questions severity (0-100) and frequency (0-100). **Note: the AVERAGE value of severity and frequency scores will be used for verifying inclusion criterion #2 at Day 0 visit.**

#### **7.1.3 Best corrected distance visual acuity (BCDVA):**

Refraction and visual acuity measurements will be performed for all patients by trained vision examiners only. Refraction should be conducted prior to visual acuity testing to obtain best-corrected vision as described below. Best-corrected visual acuity is measured at Day 0 Baseline Visit, Week 8 Visit and at Week 12 Visit using standard charts, lighting, and procedures. Best correction is determined by careful refraction at that visit according to the standard protocol for refraction as described below.

## **Equipment**

Refraction equipment required includes:

- Retroilluminated Light box and ETDRS 4 metre distance acuity chart set
- Trial lens frames
- Trial lens set with plus or minus cylinder lenses
- Jackson cross-cylinders of 0.25, 0.50, and 1.00 diopters
- Pinhole occluder
- Tissues or eye pads and tape
- A 1 metre rigid measuring stick

Visual acuity charts: Chart 1 is used for testing the visual acuity of the RIGHT eye; Chart 2 for testing the LEFT eye; and Chart R (or 3) for refraction only. Patients should not be allowed to see any of the charts before the examination.

A distance of 4 metres is required between the patient's eyes and the visual acuity chart. With the box light off, not more than 15 foot-candles of light (161.4 Lux) should fall on the centre of the chart. To measure the amount of light, the room is set up for visual acuity testing, but with the box light off. The light metre is placed at the fourth line from the top of the chart, with its back against the chart and the reading is taken. If more than one line available for testing visual acuity, the visual acuity of an individual patient should be measured in the same line at each visit, if possible. If different lines are used to test visual acuity, they must each meet the same standards.

Retroilluminated ETDRS charts are used in this trial. The illuminator box will be either wall-mounted or mounted on a stand. The light box should be mounted at a height such that the top of the third row letter is 49 + 2 inches from the floor.

The visual acuity light box is equipped with two General Electric 20-watt fluorescent tubes and ballast. Each tube is partly covered by a 14-inch fenestrated sleeve, which is centred on the tube and open in the back. This serves as a "baffle" to produce even illumination over the testing chart. Because the illumination of fluorescent tubes diminishes by 5 percent during the first 100 hours and by another 5 percent during the next 2000 hours, new tubes should be kept on for 4 days (96 hours) continuously, and should be replaced once a year.

A sticker should be placed on the back of the light box, indicating the date when the present tubes were installed. A spare set of burned in bulbs should be available on site.

## **Detailed instructions for VA assessment**

As a reminder, Charts 1, 2 and R (or 3) are used for testing the right eye, left eye, and refraction, respectively. Patients should not see the charts until the test begins. The lens correction from the patient's refraction should be in the trial frame worn by the patient.

All eyes must be tested at 4 metres first, even if the refraction was performed at 1 metre.

The patient should be seated comfortably directly in front of the chart so that the eyes remain at the 4 metre distance. Testing always begins with the right eye. The fellow eye should be occluded with a folded tissue or eye pad lightly taped over the eye behind the trial frame serves as an effective occluder that allows eccentric fixation without inadvertent use of the covered

eye. After testing the right eye, occlusion of the right eye should be done BEFORE Chart 2 is put up for testing the left eye.

The patient is asked to read the letters slowly, approximately one letter per second. The patient should be told that only one chance is given to read each letter, but may change their mind before moving to the next letter. If the patient is unsure about the identity of the letter, then the patient should be encouraged to guess.

The patient should begin by reading the top line of the chart and continue reading every letter on each smaller line, from left to right on each line. The patient should be encouraged to continue reading even if making mistakes. Each letter read is counted. The examiner circles every correct letter read and totals each line and the whole column (0 if no letters are correct) on the provided VA worksheet. An X is put through letters read incorrectly. Letters, for which no guess was attempted, are not marked. When a patient reaches a level where he/she cannot guess, the examiner may stop the test, provided that the patient has made errors on previous guesses, which is a clear indication that the best visual acuity has been obtained.

When a patient cannot read at least 20 letters on the chart at 4 metres, the patient is tested at 1 metre. The distance from the patient to the chart should be measured again using the rigid one metre stick. The distance is measured from the outer canthus to the centre of the fourth letter (right eye) or the second letter (left eye) of the third line of the chart. The spherical correction in the trial frame should be changed by adding +0.75 to correct for the closer test distance. The patient may fixate eccentrically or turn or shake his/her head to improve visual acuity. Particular care should be taken to make sure the patient does not move forward when testing at 1 metre. The patient should be reminded to blink.

The examiner should not tell the patient if a letter was identified correctly. The patient may be encouraged by neutral comments, such as “good,” “next,” and “OK.”

The examiner should not stand close to the chart during testing. Attention should be focused on the patient and the VA worksheet. If the patient has difficulty locating the next line to read, the examiner may go up to the chart and point briefly to the next line to be read, but then must move away from the chart.

When 20 or more letters are read at 4 metres the visual acuity score for that eye is recorded as the number of letters correct at 4 metres plus 30 (refer to the VA worksheet). The patient gets credit for the 30 letters at 1 metre even though they did not have to read them. Otherwise, the visual acuity score is the number of letters read correctly at 1 metre plus the number, if any, read at 4 metres. If no letters are read correctly at either 4.0 metres or 1 metre, then the visual acuity score is recorded as “0.”

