#### **11.2 Adverse Events of Special Interest (Sight-threatening Events)**

The following adverse events are considered to be of special interest and by default shall be reported as SAEs (medically important criteria):

- Adverse Events that caused a decrease in visual acuity of >30 ETDRS letters or > +0.6 LogMAR (compared with the last assessment of visual acuity at the last visit) lasting >1 hour

- Adverse Events that caused a decrease in visual acuity to the level of Light Perception or worse lasting >1 hour
- Adverse Events that required surgical intervention (e.g., conventional surgery, vitreous tap or biopsy with intravitreal injection of anti-infectives, or laser or retinal cryopexy with gas) to prevent permanent loss of sight
- Adverse Events associated with severe intraocular inflammation (i.e., 4+ anterior chamber cell/flare or 4+ vitritis)
- Adverse Events that, in the opinion of the Investigator, may require medical intervention to prevent permanent loss of sight.

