The BCDVA score will be derived as the total numbers of letters, which were read correctly at 4 meter plus the total number of letters read at 1 meter as collected on the eCRF page.

When 20 or more letters are read at 4 meters the visual acuity score (i.e. BCDVA score) for that eye is recorded as the number of letters correct at 4 meters plus 30. The patient gets credit for the 30 letters at 1 meter even though they did not have to read them. If no letters are read correctly at either 4.0 meters or 1 meter, then the visual acuity score is recorded as "0."

The logMAR will be derived as $-\log$ (Snellen Equivalent result). For this derivation the Snellen equivalent result is presented as fraction as documented in the eCRF field 'Snellen Equivalent Result'. LogMAR values derived from Snellen equivalent results range from -0.3 (20/10) to 1.6 (20/800) and will be rounded by 2 decimals. An increase in logMAR reflects a worsening of visual acuity.

If for a patient only ability for counting fingers is reported, logMAR will be set to 2; if for a patient only recognition of hand motion is reported, logMAR will be set to 3 [1].

Slit lamp examination

Slit lamp examination is performed separately for each eye at Baseline, Week 4, Week 8 and Week 12 visit and is recorded on the eCRF page 'Slit Lamp Examination (Biomicroscopy)'.

Grading of the eyelids, lashes, conjunctiva, cornea, lens, iris and anterior chamber will be done according to the following scales:

Eyelid - Meibomian glands

- 0 = None (none are plugged).
- 1 = Mild (1 to 2 glands are plugged).
- 2 = Moderate (3 to 4 glands are plugged).
- 3 = Severe (All glands are plugged).

Eyelid - Erythema

- 0 = None (normal).
- 1 = Mild (redness localized to a small region of the lid(s) margin OR skin).
- 2 = Moderate (redness of most or all lid margin OR skin).
- 3 = Severe (redness of most or all lid margin AND skin).
- 4 = Very severe (marked diffuse redness of both lid margin AND skin).

Eyelid - Edema

- 0 = None (normal).
- 1 = Mild (localized to a small region of the lid).
- 2 = Moderate (diffuse, most or all lid but not prominent/protruding).
- 3 = Severe (diffuse, most or all lid AND prominent/protruding).
- 4 = Very severe (diffuse AND prominent/protruding AND reversion of the lid).

Lashes

- 0 = Normal
- 1 = Abnormal

Conjunctiva – Erythema

- 0 = None (normal).
- 1 = Mild (a flush reddish color predominantly confined to the palpebral or bulbar conjunctiva).

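### No limit is stated on the letters counted at 1 metre, so the BCDVA letter score can jump upwards when an eye drops below 20 letters at 4 metres, distorting change from baseline in either direction

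*Protocol*

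**What the plan says.** The detailed acuity instructions in Protocol 7.1.3 set the trigger for the shorter distance: "When a patient cannot read at least 20 letters on the chart at 4 metres, the patient is tested at 1 metre". Scoring then has two branches.

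- **20 or more letters at 4 m.** The score is the 4 m count plus 30. The reason given is: "The patient gets credit for the 30 letters at 1 metre even though they did not have to read them".
- **Fewer than 20 letters at 4 m.** "the visual acuity score is the number of letters read correctly at 1 metre plus the number, if any, read at 4 metres". No maximum is attached to the 1 m count.

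On how far to read, the same instructions say: "The patient should begin by reading the top line of the chart and continue reading every letter on each smaller line". They give no separate stopping point for 1 m.

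SAP 7.2.8 has the score "derived as the total numbers of letters, which were read correctly at 4 meter plus the total number of letters read at 1 meter", using the counts on the eCRF page. It then repeats the 30-letter credit for eyes with 20 or more letters. It sets no limit on the 1 m total either.

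Protocol 11.2 lists among the sight-threatening events a "decrease in visual acuity of >30 ETDRS letters or > +0.6 LogMAR". SAP 9.6.3 summarises the letter score, logMAR and their changes from baseline by treatment group and visit.

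**The concern.** A fixed credit of 30 is coherent only if 30 is also the most that an eye can earn at 1 m. If an eye below the threshold is credited with everything it reads at 1 m, letters are counted that the other branch leaves out, and the two branches do not meet at 20. The score is then no longer monotone in acuity: a slightly worse eye can score well above a slightly better one.

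The letter score is tabulated as a safety measure, as change from baseline by arm. A derivation that follows the SAP sentence literally could record a deterioration as stability or improvement, or the reverse, in the low-vision eyes where acuity matters most for safety.

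**Working it through.** **Inputs**

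- Threshold for 1 m testing: fewer than 20 letters at 4 m (Protocol 7.1.3).
- Credit for the 1 m part at or above the threshold: 30 letters (Protocol 7.1.3, SAP 7.2.8).
- Below the threshold: 4 m letters plus 1 m letters, no maximum (Protocol 7.1.3, SAP 7.2.8).
- Scale: 30 letters paired with 0.6 logMAR (Protocol 11.2), so 0.6 / 30 = 0.02 logMAR per letter.

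**Step 1: reproduce the 30-letter credit.** Moving from 4 m to 1 m changes the visual angle by a factor of 4. log10(4) = 0.602, and 0.602 / 0.02 = 30.1 letters. The credit of 30 agrees with the documents' own scale.

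**Step 2: the two branches.** Let L be the letters read at 4 m. By Step 1 the same eye is expected to read about L + 30 at 1 m, if the chart has that many letters.

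- L of 20 or more: score = L + 30.
- L below 20, as written: score = L + (L + 30) = 2L + 30.
- L below 20, with the 1 m part limited to 30: score = L + 30.

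The excess as written is L, so it runs from 0 at L = 0 to 19 at L = 19.

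| Letters at 4 m | Score as written | Score with 30-letter limit |
|---|---|---|
| 20 | 50 | 50 |
| 19 | 68 | 49 |
| 15 | 60 | 45 |
| 10 | 50 | 40 |
| 5 | 40 | 35 |
| 0 | 30 | 30 |

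**Step 3: effect on change from baseline**

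| Letters at 4 m, baseline to follow-up | True change | Scores as written | Recorded change |
|---|---|---|---|
| 20 to 19 | -1 | 50 to 68 | +18 |
| 20 to 10 | -10 | 50 to 50 | 0 |
| 38 to 19 | -19 | 68 to 68 | 0 |
| 50 to 19 | -31 | 80 to 68 | -12 |
| 15 to 5 | -10 | 60 to 40 | -20 |
| 19 to 20 | +1 | 68 to 50 | -18 |

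A fall from b (20 or more) to L (below 20) is recorded as (2L + 30) - (b + 30) = 2L - b, when the true change is L - b. It is therefore understated by L. A change wholly below 20 is doubled.

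**Step 4: sensitivity to the 1 m count.** For an eye reading 19 letters at 4 m, compared with the score of 50 for an eye reading 20:

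| Letters counted at 1 m | Score | Difference from 50 |
|---|---|---|
| 30 | 49 | -1 |
| 31 | 50 | 0 |
| 39 | 58 | +8 |
| 44 | 63 | +13 |
| 49 | 68 | +18 |

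The upward jump disappears only if the 1 m count stops at about 30 or 31.

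**The case against.** The strongest reply is that a limit is probably intended. The protocol refers to the 1 m part as if it were a set of 30 letters, and it sends the examiner to a visual acuity worksheet. The SAP takes its counts from the eCRF. If either form provides only 30 letters at 1 m, the discontinuity does not arise. Neither form is available here, so this cannot be excluded. It stands as a condition on the finding, but does not remove it: no sentence in either document imposes the limit, and a programmer working from SAP 7.2.8 alone would code the plain sum.

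The instruction to keep reading down the chart is also given while the 4 m test is being described. Carrying it over to 1 m is an inference, although no other reading rule is supplied for that distance.

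A reader might infer two stronger conclusions. The documents support neither.

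- **That the error always hides harm.** The excess is L, so it vanishes in the very worst eyes. Losses within the range below 20 letters are exaggerated (15 to 5 is recorded as a fall of 20), and a one-letter improvement from 19 to 20 appears as a loss of 18. The distortion runs both ways.
- **That sight-threatening events would be missed.** The criterion in Protocol 11.2 has a logMAR alternative; a 31-letter loss is 31 x 0.02 = 0.62 logMAR, which meets it. SAP 7.2.8 identifies these events for analysis from a ticked eCRF box and does not use the derived letter score.

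There are further safeguards. LogMAR is derived separately from the Snellen equivalent and summarised alongside the letter score. Listing 16.2.9-1.2 shows score, Snellen and logMAR for each patient, so a discordant eye could be noticed.

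**Conclusion.** The point holds as a defect in a stated derivation rule. Followed literally, Protocol 7.1.3 and SAP 7.2.8 give a letter score that is not monotone at 20 letters: 50 at the threshold and about 68 one letter below it. Change from baseline can be wrong in size or sign, in either direction.

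The size rests on three assumptions: that an eye reads about 30 more letters at 1 m than at 4 m, which the 30-letter credit and the 30-letter/0.6-logMAR pairing imply; that the chart has at least 49 letters, needed for the full 18-letter jump; and that the worksheet or eCRF does not already limit the 1 m count.

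The reach is narrow. BCDVA is a descriptive safety measure, and the safety endpoint is TEAEs. The primary and co-primary endpoints and the sample size are untouched, as are the Snellen-derived logMAR and the special-interest classification. Few eyes are likely to fall below 20 letters at 4 m, and the documents give no figure for how many. Such eyes are possible, though: entry allows acuity down to 0.1 decimal, and SAP 7.2.8 makes provision for logMAR up to 1.6 and for counting fingers and hand motion. The point should be corrected because it is a cheap repair to a safety derivation; it does not threaten the trial's conclusions.

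**What to change.** State in Protocol 7.1.3 and SAP 7.2.8 that at most 30 letters count at 1 m, consistent with the 30-letter credit. Define the score as:

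- fewer than 20 letters at 4 m: letters at 4 m + min(30, letters at 1 m);
- 20 or more letters at 4 m: letters at 4 m + 30.

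Nineteen letters at 4 m then scores 49 and twenty scores 50, so the scale is continuous.

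Confirm that the worksheet and the eCRF page match. If they already restrict the 1 m part to 30 letters, the added wording records existing practice. If the eCRF holds only an unrestricted 1 m total, the min(30, total) rule can be applied to the counts already collected, as a close approximation to counting the first 30 letters.

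The cost is one sentence in each document, one line of derivation code and a check of two forms. No new data are needed.

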#### **7.1.4 Slit-lamp examination (SLE)**

The slit lamp examination must be performed before the instillation of any dilating or anesthetic eye drops or the fluorescein agent.

The patient will be seated at the slit lamp while being examined. Eyelids, lashes, conjunctiva, cornea, lens, iris and anterior chamber will be evaluated.

### **7.1.5 Tear Film Break Up Time (TFBUT)**

TFBUT will be measured by determining the time to tear break-up. The TFBUT will be performed after instillation of 5 µl of 2% sodium fluorescein solution into the inferior conjunctival cul-de-sac of each eye. The patient will be instructed to blink several times to thoroughly mix the fluorescein with the tear film. In order to achieve maximum fluorescence, the examiner should wait approximately 30 seconds after instillation before evaluating TFBUT. With the aid of a slit lamp at 10X magnification using cobalt blue illumination, the examiner will monitor the integrity of the tear film, noting the time it takes to form lacunae (clear spaces in the tear film) from the time that the eye is opened after the last blink. This measurement will be performed within 10 seconds maximum. The TFBUT will be measured twice during the first minute after the instillation of the fluorescein. If the 2 readings differ by more than 2 seconds a third reading is taken.

The TFBUT value will be the average of the 2 or 3 measurements.

Relevant TFBUT findings will be entered in the eCRF.

### **7.1.6 Corneal sensitivity**

For the assessment of corneal sensation the Luneau Cochet-Bonnet aesthesiometer (Western Ophthalmics Corporation©) should be used.

The Cochet-Bonnet aesthesiometer contains a thin, retractable, nylon monofilament that extends up to 6 cm in length. Variable pressure can be applied to the cornea by adjusting the monofilament length. The monofilament length ranges from 6 to 0.5 cm. As the monofilament length is decreased the pressure increases from 11 mm/g to 200 mm/g.

Corneal sensation will be measured in both eyes in each of the four quadrants of the cornea using the Cochet Bonnet aesthesiometer before the instillation of any dilating or anesthetic eye drops.

Steps for using the Cochet Bonnet aesthesiometer: extend the filament of the aesthesiometer to full length of 6 cm. Slowly advance the monofilament towards the eye until the tip perpendicularly touches the corneal surface. Continue to exert a slight pressure until obtaining an inflection deviation of the filament of about 4% (i.e. the first visible inflection). If a positive reaction to the touch of cornea is elicited proceed to step 3. If a positive reaction is not achieved proceed to step 2. (NOTE: A positive response is any action indicating corneal sensation whether communicated verbally or physically).

Retract the filament incrementally in 0.5 cm and repeat this step until the patient gives a positive reaction indicating that the contact of the monofilament on the cornea has been sensed. (NOTE: The shorter filament lengths indicate decreased corneal sensation).

Record the length of the filament in cm at which the patient sensed the contact with the cornea.

Repeat steps 1-3 in each of the 4 corneal quadrants (superior nasal, inferior nasal, superior, temporal and inferior temporal) in the study eye(s) and in each of the 4 corneal quadrants of the other eye (not the study eye, if applicable).

To clean the instrument, please refer to your national standards for devices that contact the eye and tears or follow the suggested manufacturer's recommendations.

The length of the filament in cm at which the patient corneal sensation was observed for the tested area of the cornea will be entered into the eCRF.

Corneal sensitivity findings will be entered in the eCRF.

#### **7.1.7 Ocular surface staining (NEI score)**

As grading scale of the corneal and conjunctiva damage, the NEI/Industry Workshop guidelines will be used. The cornea is divided into five sectors (central, superior, inferior, nasal and temporal), each of which is scored on a scale of 0–3, with a maximal score of 15. Both nasally and temporally, the conjunctiva is divided into a superior paralimbal area, an inferior paralimbal area and a peripheral area with a grading scale of 0–3 and with a maximal score of 9 for the nasal and temporal conjunctiva.

Ideally the grading should be performed between one and four minutes after staining. For a better reading it is also essential not to use an intense illumination beam, which may reduce the contrast and lead to an underestimation of grading

